#### **Expansion cohort:**

An additional expansion cohort of 12 patients will be enrolled at the "potential" recommended phase II dose (RP2D).

If a radiation-related (possible, probable, or definite) death (grade 5 toxicity) occurs, enrollment will be suspended and continuation of the study will be reassessed by the DSMC.

Unacceptable radiation-related toxicity (possible, probable, or definite) is defined as grade 3, 4, or 5 adverse events, excluding grade 3 adverse events that resolve or down grade to grade 2 within 14 days.

Unacceptable radiation-related toxicity (possible, probable, or definite) is expected

to occur in no more than 10% of patients. If there is evidence that the true rate of this toxicity exceeds 20%, then the study should be suspended or possibly terminated early. Specifically, we suggest as a guideline for early termination a posterior probability of 90% or higher that the true rate exceeds 20%. The table below shows specific instances where this guideline is met, suggesting early termination, and due to evidence of excessive toxicity.

Number (%) of patients experiencing unacceptable radiation-related toxicity #	Total patients evaluated
3	3 to 5
4	6 to 9
5	10 to 12

#:Radiation-related toxicity (possible, probable, or definite) is defined as grade 3 or higher adverse events, excluding grade 3 adverse events that resolve or down grade to grade 2 within 14 days.

To illustrate the stopping guidelines, suppose that 5 evaluable patients in the expansion cohort have been assessed for radiation-related toxicity and 3 of them have experienced grade 4 unacceptable toxicity. (See row 1 of the above table.) Under this circumstance, the observed rate of unacceptable toxicity is 60%, resulting in a posterior probability of 92.7% (not shown) that the true underlying rate exceeds 20%, thereby suggesting early termination.

Posterior probabilities for the above table are calculated under a weak prior beta distribution with parameters  $\beta_1 = 0.2$  and  $\beta_2 = 1.8$ , which corresponds to an expected unacceptable radiation-related toxicity rate of 20% based on very limited information, roughly equal to having studied 2 patients. This prior distribution implies also a priori chance of only 18% that true rate is 20% or greater.

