**Dose level II: 25 Gy total (2.5 Gy for 10 fractions) (Starting Dose)**

Dose level III: 30 Gy total (3.0 Gy for 10 fractions)

Dose level IV: 35 Gy total (3.5 Gy for 10 fractions)

The patients will be receiving postoperative NAC irradiation using electrons **starting at Dose level II**. Dose levels will be escalated by 0.5 Gy per fraction for an overall 5 Gy increase per level up to 3.5 Gy per fraction and a total dose of 35 Gy. **Evaluable patients** will be defined as any eligible patient that begins NAC irradiation treatment.

DLT (dose-limiting toxicity), as defined in section 4.2.6, will be evaluated during radiation treatment period plus an **additional observation period of 30 days** following completion of NAC radiation.

We propose a **modification of standard dose-escalation design, treating cohorts of 2 to 6 patients per dose level of NAC irradiation**. The main features of the proposed escalation design is that (1) no more than 2 patients will experience DLT at a given radiation dose and (2) escalation to a higher dose occurs only after a cohort of 6 patients have been evaluated at a given radiation dose.

Dose escalation/de-escalation rules	
Number of patients with DLT at a given dose level	Escalation Decision Rule
0 or 1 out of 6 patients	Enter 6 patients at the next higher dose level.
2 out of 2 to 6 patients	Dose escalation stops. However, if the dose tested is dose level II, the starting dose level, then de-escalation occurs. In this case, dose level I will be tested in 2 to 6 patients.
The highest dose tested at which $\leq 1$ out of 6 patients experiences DLT will be declared the MTD and it will be the recommended phase II dose .	

Thus, as stated in the dose escalation/de-escalation rules above, if 0 or 1 patient experiences DLT (as defined in section 4.2.6) among 6 patients, the dose level will be judged to be acceptable. If this occurs, then a new cohort of 2 to 6 patients will be accrued at the next higher dose level. If 2 patients experience DLT among 2 to 6 patients at a given dose level, then the corresponding dose will be declared to be unacceptable. If the **starting dose level** (dose level II) proves to be unacceptable, then de-escalation occurs to dose level I and 2 to 6 patients will be enrolled at dose level I.

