### 10.3.3 Safety: Early stopping due to surgery-related toxicity

We propose the following guidelines for the DSMC in its review of accumulating data on surgery-related toxicity. These guidelines were developed using Bayesian methods, which can be applied at any stage of enrollment without pre-specification of the number of interim analyses to be performed, or the number of patients evaluable for toxicity or survival at the time such assessments are made (26,27). Under the Bayesian method, we assign a prior probability (level of belief at the start of the trial) to a range of possible values for the true rate. As data on treated patients become available, this probability distribution is revised and the resulting posterior probability becomes the basis for recommending either early termination or continuation of the study. In the sections that follow, we provide specific stopping guidelines based on posterior probabilities for interim monitoring of surgery-related toxicity over the course of this trial. Underlying assumptions for the prior distribution are also presented.

If a surgery-related (possible, probable, or definite) death (grade 5 toxicity) occurs, enrollment will be suspended and continuation of the study will be reassessed by the DSMC.

Unacceptable surgery-related toxicity (possible, probable, or definite) includes grade 3-4 bleeding, infection, NAC necrosis, and any unexpected grade 3.

Unacceptable surgical-related toxicity (possible, probable, or definite) is expected to occur in no more than 10% of patients. If there is evidence that the true rate of this toxicity exceeds 20%, then the study should be suspended or possibly terminated early. Specifically, we suggest as a guideline for early termination a posterior probability of 90% or higher that the true rate exceeds 20%. The table below shows specific instances where this guideline is met, suggesting early termination, and due to evidence of excessive toxicity.

Number (%) of patients experiencing unacceptable surgery-related (possible, probable, or definite) toxicity	Total patients evaluated
3	3 to 5
4	6 to 9
5	10 to 12
6 (55 to 60%)	13 to 16
7	17

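### The Bayesian stopping tables in 10.3.2 and 10.3.3 leave out 2 events in 2 patients, which meets the plan's own 90% guideline (posterior 93.2%)

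*Combined protocol and SAP*

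**What the plan says.** The expansion-cohort part of section 10.3.2 gives the monitoring rule for radiation-related toxicity in words: "we suggest as a guideline for early termination a posterior probability of 90% or higher that the true rate exceeds 20"%. Section 10.3.3 repeats it for surgery-related toxicity. Each section then gives a table, which 10.3.3 introduces as follows: "The table below shows specific instances where this guideline is met, suggesting early termination, and due to evidence of excessive toxicity".

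Both tables open with 3 events among 3 to 5 evaluated patients. They go on to 4 events for 6 to 9 patients and 5 events for 10 to 12. The surgery table adds 6 events for 13 to 16 patients and 7 events for 17.

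Both sections state a beta prior with parameters 0.2 and 1.8. Both use 3 events in 5 patients as the worked example ("See row 1 of the above table"), "resulting in a posterior probability of 92.7% (not shown) that the true underlying rate exceeds 20%, thereby suggesting early termination".

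Neither section sets a minimum number of evaluated patients. Section 10.3.3 describes the Bayesian approach as one "which can be applied at any stage of enrollment without pre-specification of the number of interim analyses to be performed".

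**The concern.** From the third patient on, the tables have no gaps and read as a complete boundary. A committee member would naturally use them as a look-up and take the absence of a row for two patients to mean that no result at that point calls for action. The written criterion says otherwise, because 2 events in 2 patients pass the 90% threshold. They pass it by slightly more than the 3-of-5 case that the plan chose to illustrate early termination.

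What is at stake is one early look. If both of the first two evaluated patients have unacceptable toxicity, the written guideline gives a signal and the table gives none.

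**Working it through.** **Inputs.** The prior Beta(0.2, 1.8), the 20% rate limit and the 90% threshold come from 10.3.2 and are repeated in 10.3.3. The printed rows are those described above.

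**Formula.** After x events in n patients the posterior is Beta(0.2 + x, 1.8 + n − x). The guideline is met when P(rate > 0.20) under that posterior is at least 0.90.

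**Reproducing the plan's own figures.**
- Prior: P(rate > 0.20) under Beta(0.2, 1.8) = 17.5%. The plan states 18%.
- 3 of 5: P(rate > 0.20) under Beta(3.2, 3.8) = 92.7%. The plan states 92.7%.

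**Checking the printed rows.** For each row, the printed count must reach 90% at the largest n in the row, where the posterior is lowest. One event fewer must fall short at the smallest n, where it would be highest.

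| Printed row | Printed count at largest n | One event fewer at smallest n |
|---|---|---|
| 3 events, n = 3 to 5 | 3 of 5: 92.7% | 2 of 3: 86.9% |
| 4 events, n = 6 to 9 | 4 of 9: 90.4% | 3 of 6: 88.6% |
| 5 events, n = 10 to 12 | 5 of 12: 92.0% | 4 of 10: 86.9% |
| 6 events, n = 13 to 16 | 6 of 16: 91.3% | 5 of 13: 89.4% |
| 7 events, n = 17 | 7 of 17: 95.9% | 6 of 17: 88.8% |

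Every printed row is the exact minimum boundary.

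**Below n = 3.**
- 1 of 1: Beta(1.2, 1.8) gives 74.3%. The guideline is not met.
- 2 of 2: Beta(2.2, 1.8) gives 93.2%. The guideline is met, and no row lists it.

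So 2 of 2 is the only early entry missing.

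**Sensitivity to the prior.** The text describes the prior as one "which corresponds to an expected unacceptable radiation-related toxicity rate of 20% based on very limited information", but Beta(0.2, 1.8) has mean 0.2 / (0.2 + 1.8) = 10%. If a 20% mean with the same weight was intended, Beta(0.4, 1.6), then 2 of 2 gives 95.7% and still meets the guideline. That prior does not reproduce the printed figures: it gives 94.8% for 3 of 5 and a prior tail of 36.1%. The tables were therefore evidently built on Beta(0.2, 1.8).

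**How often it arises.** The chance that both of the first two patients have an event is the square of the true rate p: 1% at p = 10%, 4% at 20%, 9% at 30% and 16% at 40%.

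**Effect on stopping.** This is exact enumeration with a check after every patient, assuming independent patients with a constant rate.

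| True rate | 12 patients, as printed | 12 patients, with 2 of 2 | 17 patients (surgery), as printed | 17 patients (surgery), with 2 of 2 |
|---|---|---|---|---|
| 10% | 1.5% | 2.2% | 1.6% | 2.3% |
| 30% | 36.0% | 37.7% | 43.6% | 45.0% |

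At 20% the 12-patient figure moves from 12.5% to 14.1%, and at 40% from 63.5% to 64.7%.

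**The case against.** The strongest reply is that rule and table do not contradict each other. The rule is stated in words and already covers 2 of 2. The table is introduced as showing instances where the rule is met, so it does not claim to be exhaustive, and it prints no instruction to continue at n = 2. Section 10.3.1 offers these guidelines for the committee's consideration and has the research team monitor adverse events continuously. A related death suspends enrollment whatever the table says. All of this stands. It makes the defect an incomplete list rather than a wrong rule. It does not remove the defect, because the list is otherwise complete and a reader has no reason to look behind it.

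Two stronger readings are tempting, and the documents support neither.

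- A reader might infer that the whole boundary is set one event too high. It is not, since every row from n = 3 is the exact minimum. After 2 of 2, a third event gives 3 of 3, which the table lists. A third patient without an event gives 2 of 3 (86.9%), which no longer meets the guideline. Table and criterion agree again after one further evaluated patient.
- A reader might set the tables against the dose-finding rule in 4.2.5, which acts "If 2 patients experience DLT among 2 to 6 patients at a given dose level". That rule uses dose-limiting toxicity, a different endpoint, and governs escalation. A different early threshold in the expansion cohort or for surgery is not in itself an inconsistency.

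Two further explanations can be set aside. Text extraction did not lose an earlier row, because both worked examples place 3 of 5 in row 1. A minimum of three evaluated patients may have been intended, but neither section says so. The remark about applying the method at any stage appears only in 10.3.3 and describes Bayesian methods in general, so it is supporting evidence and not proof that a look at n = 2 was planned.

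**Conclusion.** The point holds as a minor discrepancy. Under the stated prior, 2 events in 2 patients give a 93.2% posterior probability that the rate exceeds 20%. That meets the 90% guideline, yet both tables omit it and no minimum number evaluated is given.

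The discrepancy is confined to the second evaluated patient, and no printed row needs to change. At the true rates examined (10% to 40% for 12 patients; 10% and 30% for 17), listing the entry raises the stopping probability by less than 2 percentage points.

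The posterior figure rests only on the stated prior and criterion. The stopping probabilities also assume independent patients, a constant rate and a check after every patient.

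**What to change.** Make table and criterion agree in both 10.3.2 and 10.3.3, in one of two ways:

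- list 2 events in 2 evaluated patients as a further instance that meets the guideline; or
- state that the guideline is applied from the third evaluated patient onward.

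The choice belongs to the sponsor and the monitoring committee. The first costs one row in each table and raises the false-stop probability at a true 10% rate by about 0.7 percentage points (1.5% to 2.2% over 12 patients, 1.6% to 2.3% over 17). The second costs one sentence in each section and leaves the tables' operating characteristics as they are.

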### 10.3.3 Safety: Early stopping due to surgery-related toxicity

We propose the following guidelines for the DSMC in its review of accumulating data on surgery-related toxicity. These guidelines were developed using Bayesian methods, which can be applied at any stage of enrollment without pre-specification of the number of interim analyses to be performed, or the number of patients evaluable for toxicity or survival at the time such assessments are made (26,27). Under the Bayesian method, we assign a prior probability (level of belief at the start of the trial) to a range of possible values for the true rate. As data on treated patients become available, this probability distribution is revised and the resulting posterior probability becomes the basis for recommending either early termination or continuation of the study. In the sections that follow, we provide specific stopping guidelines based on posterior probabilities for interim monitoring of surgery-related toxicity over the course of this trial. Underlying assumptions for the prior distribution are also presented.

If a surgery-related (possible, probable, or definite) death (grade 5 toxicity) occurs, enrollment will be suspended and continuation of the study will be reassessed by the DSMC.

Unacceptable surgery-related toxicity (possible, probable, or definite) includes grade 3-4 bleeding, infection, NAC necrosis, and any unexpected grade 3.

Unacceptable surgical-related toxicity (possible, probable, or definite) is expected to occur in no more than 10% of patients. If there is evidence that the true rate of this toxicity exceeds 20%, then the study should be suspended or possibly terminated early. Specifically, we suggest as a guideline for early termination a posterior probability of 90% or higher that the true rate exceeds 20%. The table below shows specific instances where this guideline is met, suggesting early termination, and due to evidence of excessive toxicity.

Number (%) of patients experiencing unacceptable surgery-related (possible, probable, or definite) toxicity	Total patients evaluated
3	3 to 5
4	6 to 9
5	10 to 12
6 (55 to 60%)	13 to 16
7	17

To illustrate the stopping guidelines, suppose that 5 evaluable patients have been assessed for surgical-related toxicity and 3 of them have experienced grade 4 unacceptable toxicity. (See row 1 of the above table.) Under this circumstance, the observed rate of unacceptable toxicity is 60%, resulting in a posterior probability of 92.7% (not shown) that the true underlying rate exceeds 20%, thereby suggesting early termination.

Posterior probabilities for the above table are calculated under a weak prior beta distribution with parameters  $\beta_1 = 0.2$  and  $\beta_2 = 1.8$ , which corresponds to an expected unacceptable surgery-related toxicity rate of 20% based on very limited information, roughly equal to having studied 2 patients. This prior distribution implies also a priori chance of only 18% that true rate is 20% or greater.

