### **6.2 General risks of Breast Reconstruction with Implants or Autologous Tissue.**

The general risks of plastic surgery reconstruction include anesthetic risk, bleeding, infection, loss of the reconstructed breast with autologous tissue secondary to necrosis, capsulitis of the breast implant, cardiac and pulmonary complications and death.

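### The surgery stopping rule counts an unexpected grade 3 event but, as written, not an unexpected grade 4 event

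*Combined protocol and SAP*

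**What the plan says.** Section 10.3.3 says that unacceptable surgery-related toxicity "includes grade 3-4 bleeding, infection, NAC necrosis, and any unexpected grade 3". The number of patients with such toxicity is compared with a printed table: 3 among 3 to 5 evaluated, 4 among 6 to 9, 5 among 10 to 12, 6 among 13 to 16, and 7 among 17. The criterion behind the table is "a posterior probability of 90% or higher that the true rate exceeds 20" percent.

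Deaths are handled separately in the same section: "If a surgery-related (possible, probable, or definite) death (grade 5 toxicity) occurs, enrollment will be suspended", and the DSMC then reassesses continuation.

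The radiation rule for the expansion cohort in 10.3.2 uses the same prior, the same criterion and the same table rows up to 12 patients. Its event "is defined as grade 3, 4, or 5 adverse events", except grade 3 events that resolve or fall to grade 2 within 14 days. The footnote to that table states the range as grade 3 or higher.

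**The concern.** A toxicity boundary should not count a milder event and pass over a more severe event of the same kind. The last item in the 10.3.3 definition does this: an unexpected event qualifies at grade 3, and nothing in the sentence says it still qualifies at grade 4. No other section adds unexpected grade 4 surgical events to this count.

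This definition supplies the numerator of the plan's only numeric boundary for surgery-related toxicity. The boundary is low (3 to 7 patients), so the classification of one patient can decide whether the guideline is met. The DSMC would then have to choose between the literal definition and its presumed intent when a count is at the boundary.

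**Working it through.** **Which patients count under 10.3.3 as written**

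- Grade 3 or 4 bleeding, infection or NAC necrosis: counted.
- Unexpected grade 3 of any type: counted.
- Unexpected grade 4 of any other type: not in the list.
- Surgery-related death: separate suspension rule.

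The table counts patients, so an unexpected grade 4 is lost only when that patient has no other qualifying event. Such a patient stays in the denominator.

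**Inputs**

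- Prior: the posteriors are "calculated under a weak prior beta distribution with parameters" 0.2 and 1.8 (10.3.3). The text describes this prior as an expected rate of 20%, whereas its mean is 0.2/(0.2 + 1.8) = 10%. I used the parameters, because they reproduce the plan's figures.
- Criterion: posterior probability of at least 90% that the true rate exceeds 20% (10.3.3).
- Example: 5 patients evaluated, of whom "3 of them have experienced grade 4 unacceptable toxicity" (10.3.3).

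**Formula**

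With x counted patients among n, the posterior is Beta(0.2 + x, 1.8 + n − x), and

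P(p > 0.20 | x of n) = 1 − F(0.20; 0.2 + x, 1.8 + n − x),

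where F is the Beta distribution function.

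**Reproducing the plan**

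- Prior: P(p > 0.20) = 17.5%. The plan says: "This prior distribution implies also a priori chance of only 18% that true rate is 20% or greater". Agrees after rounding.
- 3 of 5: Beta(3.2, 3.8) gives 92.7%, as stated.
- At every n from 3 to 17, the printed count is the smallest x of at least 3 with a posterior of 90% or more.

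**Effect of one uncounted patient in the example**

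- Suppose one of the three patients has an unexpected grade 4 event and nothing else that qualifies. The count becomes x = 2 with n = 5.
- Beta(0.2 + 2, 1.8 + 3) = Beta(2.2, 4.8) gives 72.1%, below 90%. The guideline is no longer met.

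The reversal is not peculiar to n = 5. One patient short of the printed count gives 86.9% at n = 3, 72.8% at n = 9, 78.6% at n = 12, 89.4% at n = 13 and 88.8% at n = 17, all below 90%. Of all the printed rows, n = 5 gives the lowest value one patient short, so the protocol's example shows the effect at its clearest.

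**The case against.** The strongest reply is that the sentence is loosely worded rather than wrong. The surgery list is introduced by a verb that can be read as open-ended, whereas the radiation rule uses a verb of definition. Nothing suggests that anyone meant to count an unexpected grade 3 and ignore an unexpected grade 4; a drafting slip is likelier. The worked example also treats grade 4 patients as unacceptable. I accept that a slip is likely. But a count compared with a numeric boundary needs a closed definition, and none is given elsewhere. The example does not close the gap, because its patients are already labelled unacceptable and could have had named events.

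A second reply is that such an event would be seen anyway. The boundary is guidance to the DSMC, which reviews adverse events continuously (10.3.1), and serious and unexpected events go to the IRB (7.3.2.1). This stands and limits the consequence, but neither route feeds the count. Nor does the dose-limiting toxicity item for grade 4 or 5 events in 4.2.6, which covers the radiation period plus 30 days and drives dose decisions.

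Three stronger readings are tempting, and the documents do not support them.

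- *That serious risks listed in section 6 never count.* Section 6.2 lists, for example, "loss of the reconstructed breast with autologous tissue secondary to necrosis", and both 6.1.1 and 6.2 list cardiac and pulmonary complications. But 7.1.4 makes an event unexpected if either its type or its severity is unlisted, and section 6 gives no grades. A grade 3 event of a listed type can therefore be unexpected by severity and count. Deaths suspend enrollment whatever their type.
- *That the surgery rule should count every grade 3 or higher event, as the radiation rule does.* The radiation rule does not go that far, because it excludes grade 3 events that settle within 14 days. Restricting the surgical list may also be deliberate. Widening it could raise the background rate against an unchanged boundary. Checking after each patient to n = 17, the chance of crossing is 1.6% at a true rate of 10%, 6.0% at 15% and 14.8% at 20%. If a wider definition moved an acceptable rate from 10% to 15-20% (my assumption), false stops would rise about 4-fold (6.0/1.6) to 9-fold (14.8/1.6).
- *That the gap greatly lowers the trial's overall chance of stopping.* That calculation needs the share of severe events that go uncounted, and the documents give no basis for one.

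**Conclusion.** The point holds for one category: unexpected grade 4 surgery-related events. As written they fall outside the count, while unexpected grade 3 events fall inside it. The demonstrated size is one patient's classification, which moves the protocol's example from 92.7% to 72.1% and from meeting the stopping guideline to not meeting it. This rests on reading the list as complete and on the patient having no other qualifying event. The plan's prior, criterion, table and worked figure all reproduce and are not in question here. It is a wording defect in a safety rule, worth correcting, and not evidence that severe surgical events in general escape monitoring. Whether other grade 3-4 events of the types listed in section 6 should count is a separate design choice.

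**What to change.** In the 10.3.3 definition, change the last item to *any unexpected grade 3 or higher event*. Leave the three named events, the prior, the 90% criterion and the table as they are.

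The cost is a few words. The count may be slightly higher, so the guideline may be met a little sooner. An unexpected surgery-related death would then enter the count as well as suspend enrollment, which is how 10.3.2 already treats radiation-related deaths.
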